### Section E: Questions of the Impact of the Child's Health on the Parent/Caregiver and Family

#### 1. Is the parent/caregiver currently in paid employment?

No 

a. Is the parent/caregiver currently not employed because of the child's health problems?

No

Yes

Yes 

a. Since the date of the last study site visit/telephone call, how many days did the parent/caregiver miss from work because of the child's health problems?

Total number of days missed from work because of the child's health problems:  
 \_\_\_\_\_ days

b. Since the date of the last study site visit/telephone call, how much did the child's health problems affect the ability of the parent/caregiver to be productive on the job (eg, complete tasks on time, get to work on time, pay attention when at work)? If your child's health, affected work only a little, instruct the parent/caregiver to choose a low number. Please circle a number below based on the response from parent/caregiver.

Child's health had  
no effect on  
parent's/caregiver's  
work productivity

0 1 2 3 4 5 6 7 8 9 10

Child's health  
completely prevented  
the parent/caregiver  
from being productive at  
work

2. Since the date of the last study site visit/telephone call, how much has the child's health problems affected the parent's/caregiver's availability to perform normal daily activities (other than work for pay)? By normal daily activities we mean the usual activities you perform, such as working around the house, gardening, shopping, childcare, exercising, studying, etc. If the child's health problem affected activities only a little, instruct the parent/caregiver to choose a low number. Please circle a number below based on the response from parent/caregiver.

Child's health had  
no effect on  
parent's/caregiver's  
normal daily  
activities

0 1 2 3 4 5 6 7 8 9 10

Child's health  
completely prevented  
parent/caregiver from  
doing normal daily  
activities

- 3. Since the date of the last study site visit/telephone call, how much has the child's health affected the child's usual activities? If the child's health had little effect on the child's usual activities, instruct the patient/caregiver to choose a low number. Please circle a number below based on the response from parent/caregiver.**

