5.3. Exploratory Endpoints

5.3.1. Definition

For the exploratory endpoints the data will be presented using for each subject a row for each month (based on the assignment in the database), and columns presenting the data to each subsequent question of the interview.

The same lay-out will be used to provide summary statistics for endpoints as defined below by treatment group and study Month. The definitions of these endpoints are given in [Table 3](#). Parameters will be assigned to the monthly visits based on the assignment in the database.

Table 3: Calculations and Conversion Formulae (Exploratory Endpoints)

Measurement	Calculation
Subject's daily activities limited by the subject's health per Month	The parent/caregiver reports that they are not working due to the child's health problems. The answer to Questionnaire section E question 1. The result will be either "Yes" or "No" and will be calculated for Screening and each Month as based on the assignment in the database.
Percentage of days per Month the parent/caregiver missed from work due to the subject's health	This is only calculated for parents/caregivers that were working, OR not working due to the child's health problems. If the parent is not working due to the child's health problems this is set to 100%. In all other cases total number of days missed from work because of the child's health problems, divided by the end date - start date +1 of the reported Month x100% and rounded to the nearest integer. The answer to Questionnaire section E question 1.
Parent's/caregiver's productivity at work limited by the subject's health per Month	This is only calculated for parents/caregivers that were working. The extent to which the parent's/caregiver's productivity while at work was limited by the subject's health per Month. The answer to Questionnaire section E question 1b.
Subject's health problems limited the parent's/caregiver's ability to engage in normal daily activities per Month	The extent to which the subject's health problems limited the parent's/caregiver's ability to engage in normal daily activities per Month. The answer to Questionnaire section E question 2.
How much the child's health has affected the child's usual activities per Month	The extent to which the child's health affected the child's usual activities per Month. The answer to Questionnaire section E question 3.

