Impact of the subject's health problems on the parent's/caregiver's health per Month	The extent to which the subject's health problems impacted the parent's/caregiver's health per Month. The answer to Questionnaire section E question 4.
Inability of the parent/caregiver to care for other family members due to the subject's health per Month	The inability of the parent/caregiver to care for other family members due to the subject's health per Month. The answer to Questionnaire section E question 5. The result will be either "Yes" or "No".
Subject's health limited the parent's/caregiver's time spent with other family members each Month	The extent to which the subject's health limited the parent's/caregiver's time spent with other family members each Month.

	The answer to Questionnaire section E question 6. The result will be categorical as listed in the Questionnaire.
Percentage of days other family members missed from work due to the subject's health problems per Month	The percentage of days each Month that other family members missed from work due to the subject's health problems. Derived base on the Questionnaire section E question 7. Calculated as the number of days as recorded in question 7 divided by the number of days since the last study visit/telephone call. For subjects currently not in paid employment, the value will be 100% for parents/caregivers who were not employed due to the child's health problem and missing if this was not due the child's health problem.
Clinical diagnosis of eczema within the first 2 years after the RSV infection	Clinical diagnosis of eczema within the first 2 years after the RSV infection, as diagnosed by a physician and reported by the parent/caregiver. The result will be either "Yes" or "No". Derived based on the answer to Questionnaire section C until the Month 24 analysis visit.
Clinical diagnosis of allergic rhinitis within the first 2 years after the RSV infection	Clinical diagnosis of allergic rhinitis within the first 2 years after the RSV infection, as diagnosed by a physician and reported by the parent/caregiver. The result will be either "Yes" or "No". Derived based on the answer to Questionnaire section D until the Month 24 analysis visit.

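### SAP Table 3 scores a working parent's missed work on an all-days scale, assigns 100% to a parent not working because of the child, and leaves the divisor undefined

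*SAP*

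**What the plan says.** SAP 5.3.1, Table 3, defines the parent's percentage of days missed from work for two kinds of parent together: "This is only calculated for parents/caregivers that were working, OR not working due to the child's health problems".

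- For the second kind the value is fixed: "If the parent is not working due to the child's health problems this is set to 100" per cent.
- For the first kind it is calculated: the count of days lost on the child's account is "divided by the end date - start date +1 of the reported Month".

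The numerator comes from Section E, question 1a of the questionnaire (Protocol, Attachment 2): "Since the date of the last study site visit/telephone call, how many days did the parent/caregiver miss from work".

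The Table 3 row for other family members (question 7) uses a divisor in different words: "divided by the number of days since the last study visit/telephone call". That row also assigns 100% where the parent is not employed because of the child's health, and sets the value to missing where the parent is not employed for another reason.

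The first row of Table 3 already derives, as Yes/No for Screening and each Month, whether the parent is not working because of the child's health. Its label, however, refers to limits on the child's own daily activities. SAP 5.3.1 plans summary statistics for these parameters by treatment group and study Month. Protocol 2.1.2 defines the endpoint as a percentage of days in each month and mentions no assigned value.

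**The concern.** Only a day on which the parent would have worked can be missed from work, but the divisor counts every day. A working parent who misses every shift therefore scores below 100% unless they work seven days a week. A parent who has left work because of the child scores exactly 100%. The two have lost the same share of their work, yet they get different values in one variable, and that variable is then summarised by group. With 7 subjects in the whole study, one assigned 100% can move a group mean visibly.

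The same assigned value in the question 7 row is harder to interpret. That row is about days other relatives missed, but the 100% is triggered by the parent's employment status.

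The divisor is a separate matter. The SAP gives no start or end date for the reported Month, and its wording matches neither question 1a nor the question 7 row. Two programmers could build it differently.

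**Working it through.** The plan states no ceiling or expected value for this parameter, so there is no figure to reproduce.

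**Inputs**
- Numerator: days missed from work (question 1a).
- Divisor: all days of the reported Month (SAP Table 3).
- Assigned value: 100% (SAP Table 3).
- Working week: not in the documents; taken as 3 to 7 days.
- Contact interval: monthly calls with a ±7 day window (Protocol, Time and Events Schedule). Around a 30-day month, two contacts can lie 30 − 14 = 16 to 30 + 14 = 44 days apart.
- Enrolled subjects: 7 (SAP 2.4).

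**Step 1. Highest value a working parent can reach.** Ceiling = working days in the period / all days in the period × 100.

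| Working week | Average ceiling |
|---|---|
| 3 days | 3/7 = 42.9% |
| 4 days | 4/7 = 57.1% |
| 5 days | 5/7 = 71.4% |
| 6 days | 6/7 = 85.7% |
| 7 days | 7/7 = 100% |

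For a 5-day week, by length of calendar month:
- 28 days: 20/28 = 71.4%.
- 29 days: 20/29 to 21/29 = 69.0% to 72.4%.
- 30 days: 20/30 to 22/30 = 66.7% to 73.3%.
- 31 days: 21/31 to 23/31 = 67.7% to 74.2%.

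The full range is 66.7% to 74.2%.

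**Step 2. Gap to the assigned value when every shift is missed.** For a 5-day week, 100 − 74.2 = 25.8 to 100 − 66.7 = 33.3 points. For a 3-day week, 100 − 42.9 = 57.1 points on average. For a 7-day week, none.

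**Step 3. Effect on a group mean (illustration).** Take four parents who all lose every working day of a 5-day week. The documents do not give the split of the 7 subjects by group, so four is an assumption. If all four are still employed, the mean is 71.4%. If one has left work, it is (3 × 71.4 + 100)/4 = 78.6%. With two it is 85.7%, and with four 100%. The loss of work is the same throughout; only the scoring route changes.

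**Step 4. The divisor under its two readings.**
- *The interval covered by the report.* The divisor is the recall period, give or take the one day added by the formula. For 22 missed shifts over 30 days, 22/30 = 73.3% and 22/31 = 71.0%.
- *A fixed 30-day month.* After one missed call, 8 days missed over a 60-day recall gives 8/30 = 26.7%, against 8/60 = 13.3%. For a 5-day week with every shift missed, a 16-day recall (10 to 12 shifts) gives 33% to 40%. A 44-day recall (30 to 32 shifts) gives 100% to 107%. The error can go either way and can pass 100%.

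**Step 5. Does changing the divisor remove the mixed scale?** No. Over a 30-day recall, a 5-day week still tops out at 20/30 to 22/30 = 67% to 73%. The assigned 100% has to go as well.

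**The case against.** The strongest reply is that the rule is an openly stated convention. The protocol endpoint is a percentage of days each month, which points to an all-days divisor, and scheduled working days are not collected. Leaving work because of the child is the most complete form of the impact being measured, so 100% is not an absurd score. The gaps above arise only when a parent misses every shift, and they depend on a working week the documents do not give. Listings show each interview answer by subject and month, so a reader could separate assigned from calculated values. No hypothesis is tested.

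Most of this stands, and it limits the importance of the point. It does not make the two scales comparable: listings do not repair a group summary that combines them, and the protocol endpoint does not call for the assigned value.

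Two stronger readings are tempting and are not supported:
- A reader might infer that the divisor definitely covers a different period from the recall, so that percentages are inflated after a late or missed call. The documents do not establish this. SAP 2.5 places monthly reports by their entry dates, so the reported Month may well be the interval between reports, in which case the mismatch is at most one day.
- A reader might infer that the group mean reflects employment mix instead of the child's health. That goes too far, because leaving work on account of the child is itself an effect of the child's health, and working parents' values still vary with days missed.

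**Conclusion.** The point holds for the mixed scale, in both rows. In the parent's row, equal total loss of work is scored differently: 100% by assignment, against an average of 71% for a 5-day week (67-74% by calendar month) or 43% for a 3-day week. These figures assume the length of the working week and that every shift is missed, so they are the largest gaps for those weeks and not expected errors. In the question 7 row, the assigned 100% also brings the parent's employment into a variable about other relatives.

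On the divisor, the supportable finding is narrower: the term is undefined and is worded differently from question 1a and from the question 7 row. It would distort results only if a fixed or calendar month were programmed.

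This is a desirable clarification, not an essential one. The endpoint is exploratory, the analysis is descriptive, 7 subjects were enrolled, and no conclusion of the study turns on it.

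**What to change.** Change SAP Table 3 as follows:

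1. Remove the assigned 100% from the parent's row and from the question 7 row.
2. Summarise the parent's percentage for employed parents only, and label it as a percentage of calendar days.
3. Use days since the last visit or call as the divisor in both rows. For the entry report, use the recall period set in Protocol 9.1.2.
4. Report parents not employed because of the child's health as a separate yes/no count. Row 1 of Table 3 already derives it; its label needs correcting to match.

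A working-day divisor would also put full absence at 100%, but Section E, question 1 does not collect scheduled working days, so separate reporting is what the data support.

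The cost is a few lines of SAP wording and a minor programming change, with no new data. The downside is that parents who left work no longer count in the mean, so the separate count must be shown beside it; otherwise the most affected families would drop out of view.

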- f. Medication use will be monitored throughout the study from signing of the informed consent form until the last study-related activity. Parents/caregivers will be required to bring all medications to the study site visit. Additionally, parents/caregivers will be required to document on a daily basis use of all medications on a medication parent/caregiver card, which will serve as a reminder card to be used during the study site visits and during the monthly phone calls between the study site visits for recording the medication used for respiratory infections and illnesses in the eCRF by the study site personnel. Parents/caregivers will be required to return the completed parent/caregiver cards to the study sites every 3 months (eg, in person or by mail/email/fax when no study site visit is scheduled).
- g. Collection of data on wheezing, asthma, eczema, allergic rhinitis, and impact of the subject's health status on normal daily activities for subjects, parents/caregivers, and other family members using a standardized questionnaire. The questionnaire should preferably be completed by the same study site responsible person, by

interviewing the subject's parent/caregiver. Parents/caregivers will complete the wheezing and medication parent/caregiver cards on a daily basis, which will aid the study site responsible person in completing the questionnaire during the interview. Parents/caregivers will be required to return the completed parent/caregiver cards to the study sites every 3 months (eg, in person or by mail/email/fax when no study site visit is scheduled).

- h. Once per calendar month ( $\pm 7$  days) from the entry visit.
- i. Data from lung function tests and allergy tests (immunoglobulin E and skin test), if available, will be collected as supporting documentation of the diagnosis of asthma, wheezing, and atopy as reported by the parent/caregiver.
- j. Medical resource utilization will be monitored throughout the study from signing of the informed consent form until the last study-related activity and will include medical visits, emergency room visits, and hospitalizations, all for respiratory conditions only and will be recorded in the eCRF. Visits with each type of health care provider (eg, general practitioner, pediatrician, physician assistant, nurse practitioner, pulmonologist, allergist, or other) will be specified in the eCRF.

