### **Exploratory Endpoints**

The exploratory endpoints during the follow-up period are:

- The long-term impact of RSV and its treatment with lumicitabine or placebo on how the subject's health affects the normal daily activities of the subject, the parent/caregiver, and other family members as determined by:
  - The extent to which the subject's daily activities each month were limited by the subject's health.
  - The percentage of days each month that the parent/caregiver missed from work due to the subject's health.
  - The extent to which the parent's/caregiver's productivity while at work was limited by the subject's health.

- The extent to which the subject’s health problems limited the parent’s/caregiver’s ability to engage in normal daily activities.
  - The extent to which the subject’s health problems impacted the parent’s/caregiver’s health.
  - The inability of the parent/caregiver to care for other family members due to the subject’s health.
  - The extent to which the subject’s health limited the parent’s/caregiver’s time spent with other family members.
  - The percentage of days each month that other family members missed from work due to the subject’s health problems.
- Frequency of wheezing and clinical diagnosis of asthma by type of wheezing/asthma phenotype.

Refer to Section 9 for evaluations related to endpoints.

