Child's health had no effect on the child's usual activities	
 
 0	1	2	3	4	5	6	7	8	9	10	
 
	0	1	2	3	4	5	6	7	8	9	10	Child's health severely limited the child's usual activities
0	1	2	3	4	5	6	7	8	9	10			

- 4. Since the date of the last study site visit/telephone call, how much has the child's health affected the parent's/caregiver's health? If the child's health problem had little effect on the parent's/caregiver's health, instruct the patient/caregiver to choose a low number. Please circle a number below based on the response from parent/caregiver.**

Child's health had no effect on the parent's/caregiver's health	
 
 0	1	2	3	4	5	6	7	8	9	10	
 
	0	1	2	3	4	5	6	7	8	9	10	Child's health caused severe health problems for the parent/caregiver
0	1	2	3	4	5	6	7	8	9	10			

- 5. Since the date of the last study site visit/telephone call, has the child's health made it difficult for the caregiver to care for other family members?**

- No  
 Yes

- 6. Since the date of the last study site visit/telephone call, how often did the child's health limit the amount of time the parent/caregiver spent with other family members?**

- Rarely or never limited time  
 Occasionally limited time  
 Often limited time  
 Most of the time or always limited time

- 7. Since the date of the last study site visit/telephone call, how many days did other family members miss from work because of the child's health problems (eg, to stay home to care for the child or other family members, to take time off to take the child for medical visits, etc.)?**

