Total number of days that family members missed from work because of the child's health problems: \_\_\_\_ days

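### SAP Table 3 divides a question 7 total covering all other family members by calendar days, with no stated counting unit and no count of relatives, so the result need not be a true percentage

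*SAP*

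**What the plan says.** Protocol 2.1.2 lists as an exploratory endpoint "The percentage of days each month that other family members missed from work" because of the child's health. It gives no denominator and no rule for families with more than one working relative.

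The data come from Protocol Attachment 2, Section E, question 7. It asks, for the time since the last contact, "how many days did other family members miss from work", and provides one blank labelled "Total number of days that family members missed from work". Nothing in Section E asks how many other relatives there are or how many of them work.

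SAP 5.3.1 Table 3 turns the answer into a percentage: "Calculated as the number of days as recorded in question 7 divided by the number of days since the last study visit/telephone call". The same row adds a special rule, "the value will be 100% for parents/caregivers who were not employed due to the child's health problem", and sets the value to missing when the parent/caregiver is out of work for another reason. The row has no cap, no division by number of relatives and no instruction to count distinct calendar days.

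SAP 5.3.1 plans summary statistics for these items by treatment group and month, and also a display with one row per subject per month showing the interview answers. SAP 2.4 states that 7 subjects were included, and SAP 1.3 that no formal hypothesis testing is done.

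**The concern.** The numerator covers a group of people and the denominator covers the elapsed time of one. The neighbouring Table 3 row, for days the parent/caregiver missed, has a similar form, but there both parts refer to the same single person. When the form is carried over to several relatives, the units match only if question 7 was answered as distinct calendar days, and neither document says that it was.

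If the total is in person-days, the same absence per relative gives a larger value in a larger family, and the value has no ceiling at 100. A reader of a column headed as a percentage will assume a 0 to 100 scale. With so few children, one large household could move a group's monthly mean for reasons unrelated to the child's health.

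**Working it through.** The plan states no numerical value for this item, so there is no figure to reproduce. The check applies the SAP formula to plausible answers.

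**Inputs**
- Numerator: the question 7 total (Protocol Attachment 2, Section E).
- Denominator: calendar days since the last contact (SAP Table 3). The Time and Events Schedule sets telephone calls "Once per calendar month", with a 7-day window either side. I assume D = 30 days and show 23 and 37 (30 − 7 and 30 + 7).
- Number of working relatives, k: not collected. I assume 1 to 4.
- Days missed per relative, d: assumed, 5 for the main illustration.
- Working week: assumed 5 days in 7.

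**Formula on the person-day reading**

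Value = 100 × (k × d) / D

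With d = 5:

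| Relatives | D = 23 | D = 30 | D = 37 |
|---|---|---|---|
| 1 | 5/23 = 21.7% | 5/30 = 16.7% | 5/37 = 13.5% |
| 2 | 10/23 = 43.5% | 10/30 = 33.3% | 10/37 = 27.0% |
| 3 | 15/23 = 65.2% | 15/30 = 50.0% | 15/37 = 40.5% |
| 4 | 20/23 = 87.0% | 20/30 = 66.7% | 20/37 = 54.1% |

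The absence per person is the same down each column, but the value rises in proportion to k. Lighter absence gives the same pattern on a smaller scale: with d = 2 and D = 30, the values are 2/30 = 7%, 4/30 = 13% and 6/30 = 20% for one, two and three relatives.

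**When it passes 100%**

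This requires k × d > D, that is d > D/k. In 30 days, two relatives must each miss more than 30/2 = 15 days, or three must each miss more than 30/3 = 10. A 5-day week offers 30 × 5/7 = 21.4 working days, so these absences are possible but long. If every working day is missed, the maximum is 100 × k × 5/7: 71.4% for one relative, 142.9% for two and 214.3% for three. With one relative the value cannot exceed 100%.

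**The other way of counting**

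Suppose two relatives miss the same 5 days of 30. Counted as person-days, question 7 is 10 and the value is 33.3%. Counted as distinct calendar days, question 7 is 5 and the value is 5/30 = 16.7%. The same family can therefore produce either figure, a twofold difference, depending on an instruction that the form does not give. On the distinct-day count the value cannot exceed 100%.

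**Can the analysis repair it?**

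Dividing by k × D would give 5k/(30k) = 16.7% for every k, with a ceiling of 100%. This needs k, which is not recorded.

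**The special rule in the row**

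The rule depends on whether the parent/caregiver is employed, but the item is about other relatives. A family whose parent/caregiver gave up work because of the child scores 100% even if question 7 is 0. A family whose parent/caregiver is out of work for another reason is set to missing even if question 7 was answered. This mismatch needs no assumption about how days were counted.

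**The case against.** The strongest objection is that the person-day reading is an inference. The wording of question 7 does not settle whether simultaneous absences are added. The phrase for a total number of days also labels question 1a, which concerns one person, so *total* need not mean summed over people. The protocol endpoint can be read as the share of days on which relatives missed work, and on that reading the SAP denominator is valid. This stands in part. Person-days is the more natural reading of one total over several relatives, but the documents do not fix it. If families counted differently, their values are not comparable, so the counting unit still needs stating.

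The second objection is size. Values above 100% need at least two relatives with long absences and are probably uncommon. The item is one of several exploratory impact measures, nothing is tested, and the per-subject display keeps the raw answers visible. All of this stands. It limits the consequence but does not correct the formula, and the dependence on family size on the person-day reading does not require long absences.

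A reader might go further and infer that the reported values will exceed 100%, or that comparison of the treatment groups is compromised. The documents support neither. The first depends on family sizes and absences that are not known, and the second presumes an inference that the SAP does not plan.

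**Conclusion.** The point holds as a definitional defect of small consequence. SAP Table 3 divides a group total by one person's elapsed days without stating the counting unit, and the number of working relatives is not available to correct it. On the more natural, person-day reading the value scales with the number of relatives and has no upper bound at 100%. The percentages shown rest on the assumed interval, family size and days missed, and they illustrate the formula rather than predict the data.

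It would be too strong to say outright that the result is not a percentage, because the distinct-day reading is not excluded. Separately, and whichever reading applies, the rule based on the parent's/caregiver's employment does not belong in a row about other relatives.

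The primary and secondary endpoints and the safety analyses are unaffected.

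**What to change.** Change one row of SAP Table 3:

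1. Report question 7 as *total days missed from work by other family members, as reported, per 30 days covered*, computed as 30 × (question 7 total) / (days since the last contact).
2. Drop the percentage label and record this as a departure from the protocol's endpoint wording.
3. Add a footnote that the value is not adjusted for the number of relatives and that same-day absences may be counted more than once.
4. Remove the rule that sets 100% or missing from the parent's/caregiver's employment status. It does not concern other relatives and has no meaning on the new scale.

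This makes the dependence on family size visible but does not remove it, which would need a count of working relatives. Using the words *as reported* avoids committing to a person-day count that the form does not guarantee.

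Rewording question 7 is not proposed for this study: SAP 3 says that the project was stopped and that extending follow-up was not deemed useful.

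The cost is SAP wording and the programming of one exploratory item, using data already collected.
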